8.4.5.2 Clinical safety analysis

The actual values and changes from baseline in pulse/heart rate and blood pressure will be summarised using descriptive statistics. Any abnormal 12-lead ECG findings and special situations will be summarised.

8.4.5.3 Laboratory safety analysis

In case recorded, laboratory values and changes from baseline will be summarised using descriptive statistics.

8.4.5.4 Analysis of prior and concomitant treatments

The number and percentage of subjects using concomitant treatments will be summarised by pharmacological subgroup and chemical substance. The summary of prior medications will be based on data collected at initiation of the REFALS study and covering all relevant changes prior to initiation of this study.

8.4.5.5 Analysis of Suicidality

Suicidality will be summarised using descriptive statistics.

8.5 Interim analyses

No interim analysis is planned for this study.

9. DATA QUALITY ASSURANCE

9.1 Training

An initiation meeting will be arranged for the investigators and other relevant study centre personnel. This meeting will include a review of the protocol, CRF completion and study procedures.

The investigators will ensure that appropriate training relevant to the study is given to the medical, nursing and other personnel involved in the study. The investigators will also ensure that any information relevant to the conduct of the study is forwarded to other relevant study centre personnel.

9.2 Case report forms

Electronic queries about missing, misleading, incomplete or illogical data will appear in the EDC system. An audit trail within the system will track all changes/corrections made. The investigator has to confirm the content of the eCRF with an electronic signature.

9.3 Monitoring, audits and inspections

The CRO will implement a risk based monitoring strategy which will combine a centralised monitoring team of site management associates (SMAs) supported by a clinical research associate (CRA) who will perform on site visits.

In this innovative real world research model, the site relationship is streamlined from onsite and in-house CRAs to centralised (regional) SMAs. The SMAs use state-of-the-art analytical tools to combine site management, data review, query processing, and central monitoring into a single role, which reduces resource allocation and site burden. During the last interim monitoring visit for pivotal phase activities, PRA will conduct a hand-off call (Site Initiation for OLE) for each site, which would include site staff and the CRA and SMA assigned to the site.

The CRA will perform on site visits if needed in line with the risk management assessment plan and to perform close out activities at the end of the study.

The SMA/CRA will ensure that the study complies with good clinical practice (GCP) and applicable regulatory requirements and that the protocol is followed in all aspects, accurate recording of results, reporting of AEs, drug accountability and record keeping.

The study may be audited by independent representative(s) of the sponsor or inspected by the CAs. For these purposes, the study monitor, auditors and inspectors will be allowed direct access to hospital or patient records/source data of the study subjects, original laboratory data etc., as far as they are related to the study.

It is essential that the investigator and other relevant members of the study centre team are available during the monitoring visits, audits and inspections, and that they devote sufficient time to these processes.

9.4 Laboratories and other vendors

A local laboratory will be used for possible laboratory safety measurements and ECG analyses.

Details regarding spirometry and possible laboratory safety measurements and ECG analyses are presented in the separate instructions. Quality certificates are required from all safety laboratories.

In case levosimendan concentration samples are taken, bioanalytics will be performed using validated methods.

10. FURTHER REQUIREMENTS AND GENERAL INFORMATION

10.1 Investigators and study administrative structure

10.1.1 Investigators

Should the investigator transfer one of his/her responsibilities to other members of the study centre team, he/she must have this documented.

In the event of changes in key study centre team members, the responsible investigator must ensure that the successor is fully informed and capable of following the procedures.

A curriculum vitae in English must be obtained from all investigators who sign the protocol and from other relevant persons.

10.1.2 Data and safety monitoring board

No formal data and safety monitoring board (DSMB) reviews specifically for this study are planned. The DSMB of the REFALS study will review the data from this extension study until completion of the REFALS study. The DSMB may also decide to conduct further meetings to review safety data from this extension study, if clinically indicated. The duty of the DSMB is to protect the ethical and safety interests of the study subjects and all others who may possibly be exposed to study treatments.

Further details regarding the composition and responsibility of the REFALS study DSMB are presented in the DSMB charter.

10.2 Amendments to study protocol

Any change or addition to the protocol can only be made in a written protocol amendment that must be approved by the sponsor, and when required by the EC or CA. Only in the event of a need to eliminate an immediate hazard(s) to study subjects, the investigator may implement deviation from the protocol without prior approval.

Any change or addition to the approved study protocol may lead to suspension of the study or its results.

Any changes to the study protocol are subject to prior discussion with, and approval by, the sponsor and the principal investigator. As a general rule, protocol amendments should be approved according to the same procedures as the study protocol.

Amendments are regarded as substantial, where they are likely to have a significant impact on the safety, physical or mental integrity of the study subjects, or the scientific value of the study. An approval of the responsible EC or CA shall be obtained before substantial amendments may be implemented, unless local regulations are different.

If an amendment contains only minor changes (typically administrative) not affecting the safety, physical or mental integrity of the study subjects, or the scientific value of the study, the EC or CA need not to be notified and in-house approval (including approval by the principal investigator) is adequate.

10.3 Insurance

The sponsor will provide clinical trial liability insurance for study subjects in all participating countries according to local regulations.

10.4 Financial disclosure

The investigator will be required to disclose any financial arrangement whereby the value of the compensation for conducting the study could be influenced by the outcome of the study; any significant payments of other sorts from the sponsor, such as a grant to fund on-going research, compensation in the form of equipment, retainer for on-going consultation, or honoraria; any proprietary interest in oral levosimendan; any significant equity interest in the sponsor as defined in the US Code of Federal Regulations [21 CFR 54 2(b)].

In consideration of participation in the study, the sponsor will pay the investigator, or nominated payee the sums set out in the payment schedule attached to the Investigator Agreement.

10.5 Retention of records

The investigator agrees to keep the following documentation in the investigator's study file: study subject records, a subject identification list, all original signed IC forms, a copy of CRFs and records of drug dispensing.

The study files at the study centres will be stored in the respective archives for 15 years, after which the sponsor will be contacted and the possibility of future archiving will be mutually agreed upon.

10.6 Completion of the study

The end of the study is defined as the date of the last subject's last visit or last contact with the study site.

Study centres will be closed upon study completion. A study centre is considered closed when all required documents and study supplies have been collected and a study completion/termination visit has been performed.

The sponsor reserves the right to prematurely terminate the study, or recruitment to the study, for valid scientific or administrative reasons. After decision to prematurely terminate the study, the investigator must contact all participating study subjects within 7 days, and invite them for an end-of-study visit.

10.7 Reports, publications and communication of results

Statistical analysis will be performed by or under the supervision of the sponsor according to the statistical analysis plan.

The study report will be prepared by or under the supervision of the sponsor. The final report will be approved by the appropriate representatives of the sponsor and the investigators.

Orion wishes to collaborate with the investigators to publish the results as timely as possible, without compromising accuracy or industrial property rights. The preparation, submission and authorship for publications containing the study results shall be in accordance with a process determined by mutual written agreement among the sponsor and participating investigators/institutions, and in accordance with international criteria for authorship; see International Committee of Medical Journal Editors recommendations, available at <http://www.icmje.org>.

Orion remains the exclusive owner of the study data defined by the protocol.

This study will be registered in one of the acceptable registries before the enrolment of the first subject.

11. ETHICS

11.1 Ethics committee

The study protocol, subject information sheet, IC form, and all other necessary documents will be submitted to an independent EC/IRB for review according to local regulations.

The investigator is responsible for obtaining a favourable opinion from the EC/IRB for the study, submitting any amendment(s), and communicating study-related safety issues as requested by the EC/IRB. The investigator should file all correspondence with the EC/IRB in the investigator's study file. Relevant copies of this correspondence should be forwarded to the sponsor.

11.2 Ethical conduct of the study

The study will be conducted in accordance with the Declaration of Helsinki guiding physicians in biomedical research involving human subjects.

The study shall not be initiated before favourable opinion from the EC and approval from the CA has been obtained for the study.

The study will be conducted in compliance with the protocol, GCP (ICH E6[R2]) and applicable regulatory requirements. A substantial amendment shall not be implemented until the protocol amendment has received a favourable opinion from the EC and approval from the CA. Only in

case of the need to eliminate an immediate hazard(s) to study subjects, the investigator may implement deviation from the protocol without prior favourable opinion from the EC and approval from the CA for the protocol amendment.

In case of serious breaches, the MHRA GCP Inspectorate must be notified according to MHRA Guidance for the notification of serious breaches of GCP or the study protocol (see <http://www.mhra.gov.uk>).

11.3 Subject information and informed consent

The investigator will ensure that each subject candidate is fully informed about the objectives and procedures of the study. The investigator will also explain any possible risks with participating in the study and answer all questions regarding the study. After this, the subject will be given sufficient time to make a decision regarding participation in the study. In the case that the subject is unable to sign the consent form due to muscular weakness, a witness may sign the form to indicate that the subject has given oral consent to participate in the study. In such cases, the investigator must also explain the study to the witness at the same time as they explain the study to the participant. After this, the subject will be given sufficient time to make a decision regarding participation in the study.

Subjects will be informed of their right to discontinue the study at any time without their medical care or legal rights being affected. Subjects will also be informed that representatives of the sponsor or CA may inspect relevant parts of their medical records and study data.

The investigator will obtain a signed and dated consent from each subject before any study related procedures are performed. A copy of each signed and dated IC will be given to the subject. The investigator should confirm the receipt of every IC by entering the date of the consent both on the subject's CRF and also on the subject screening log and identification list.

11.4 Subject data protection

Information collected during the course of the study will be stored in a database and used in the further development of oral levosimendan and thereafter for as long as the information is relevant to patient care. The use includes the transfer of data to CAs in the European Union, the United States or other countries for the purpose of obtaining and maintaining marketing authorisations. All information is handled confidentially and according to local laws and regulations.

The study subjects can be identified in the CRFs only by study subject number, birth year and sex.

13.1 Revision history

Protocol and amendments	Date	Applies to
Clinical study protocol	07 January 2019	Global
Amendment 1	26 March 2020	Global

Country specific amendments	Date	Applies to
Amendment 1	30 April 2019	Sweden

13.2 Summary of changes

The changes incorporated in this amended protocol from the original protocol dated 07 Jan 2019 are described in the following. The modifications of the text are indicated by strikethrough (for deletions) and underline (for additions).

The following changes were made due to COVID-19 pandemic:

Section	Previous text	New text	Rationale for the change
6.5 Changes implemented due to COVID-19 pandemic	-	Whole text is new, see the section 6.5 .	New sections describing changes due to COVID-19 pandemic added

In addition,

- the table of contents was updated to reflect the headings and pagination of the current document.
- the title page, header and footer sections were updated to reflect the version details of the current document

7.12	Execution of statistical analyses	19
7.13	Software	19
8.	REFERENCES	19
9.	REVISION HISTORY.....	20
10.	APPENDICES.....	20
10.1	Medical history groups of interest	20
10.2	Adverse events of special interest.....	20

ABBREVIATIONS

AE	Adverse event
AESI	Treatment-emergent adverse event of special interest
ALS	Amyotrophic lateral sclerosis
ALSFRS-R	Revised ALS Functional Rating Scale
ALT	Alanine transaminase
ANOVA	Analysis of variance
AST	Asparate transaminase
ATC	Anatomical therapeutic chemical
BMI	Body mass index
BP	Blood pressure
CAFS	Combined assessment of function and survival
CGI	Clinical Global Impression
CI	Confidence interval
CR10	Category Ratio 10
CRF	Case report form
DSMB	Data and safety monitoring board
ECG	Electrocardiogram
eGFR	Creatinine clearance
FAS	Full analysis set
HR	Heart rate
IHSC	In-house search category
ITT	Intent-to-treat
KM	Kaplan-Meier
MedDRA	Medical Dictionary for Regulatory Activities
MMRM	Mixed model for repeated measures
NIV	Non-invasive mask ventilation

PD	Pharmacodynamic
PK	Pharmacokinetic
PP	Per-protocol
PR	Pulse rate
PT	Preferred term
RMST	Restricted mean survival time
RTSM	Randomization and trial supply management
SAE	Serious adverse event
SAP	Statistical analysis plan
SD	Standard deviation
SMQ	Standardised MedDRA Query
SOC	System organ class
SVC	Slow vital capacity
TEAE	Treatment-emergent adverse event
TESAE	Treatment-emergent serious adverse event
ULN	Upper limit of normal
VAS	Visual analogue scale

1. GENERAL REMARKS

The purpose of this document is to describe the statistical methodology for this clinical study, including also plans of analysis datasets to be used and the plans how the results will be presented.

2. OVERALL STUDY DESIGN AND PLAN

[figure not shown]
This is an open, non-randomised, uncontrolled, multicentre phase III extension study to the REFALS study.

The subjects will give informed consent (IC) to continue in this open-label extension study at the 48-week or end-of-study visit of the REFALS (or between these visits). The REFALS end-of-study visit will double as the REFALS-ES baseline visit. Visits to the study centre are flexible but occur at least every 3 months. Subject assessments will be conducted 2 weeks after starting the study treatment and after each change in the dose: such visits may be at study centre or conducted remotely where feasible (see section 6.1.3 in the protocol). A telephone contact will be performed for all subjects 6 weeks after starting the treatment.

The subject may continue the treatment as long as clinically indicated (see withdrawal criteria in section 4.5 in the protocol) or until the study ends.

An end-of-study visit will take place 14-25 days after the last study treatment administration for each subject.

The study design is presented in [Figure 1](#).

TC = telephone contact, EOS = end-of-study

¹ Dose increased to 1 mg b.i.d. if the 1 mg/day dosing was well tolerated

² Additional visit approx. 2 weeks after any dose change at visit 2

Figure 1. Study design

3. STUDY OBJECTIVES

3.1 Primary objective

The primary objective, in addition to continuing treatment for subjects in REFALS study, is to evaluate long-term safety of oral levosimendan in ALS patients.

3.2 Secondary objectives

The secondary objective is to explore long-term effectiveness of oral levosimendan in the treatment of patients with ALS, by continuing to observe rate of disease progression during the treatment.

4. STATISTICAL HYPOTHESES

No formal statistical hypotheses are specified.

5. DETERMINATION OF SAMPLE SIZE

No sample size estimation is done. The maximum number of participants is bounded by the number of subjects completing REFALS.

6. GENERAL STATISTICAL CONSIDERATIONS

6.1 Data sets to be analysed

All analyses will be performed in the safety population, including subjects who receive at least 1 dose of study treatment. No other analysis populations are planned.

6.2 Statistical issues

6.2.1 Randomization

No randomization is done in the extension study. Subjects were randomized to either levosimendan or placebo in a 2:1 ratio for the main study. That randomization will be used for reporting this study, dividing subjects into arms having received prior levosimendan or placebo.

6.2.2 Significance level and confidence intervals

Not applicable. There are no formal hypothesis tests.

6.2.3 Multiplicity

No adjustment for multiplicity is planned.

6.2.4 Intercurrent events

Not applicable.

6.2.5 Dropouts and missing data

Analyses are performed without missing data handling, in a complete-case manner.

6.2.6 Outliers

Detection of outliers will be done via visual inspection. If outliers are detected, a sensitivity analysis excluding the outliers may be performed to evaluate their impact to the results.

6.2.7 Baseline values

Planned pre-dose values from the baseline visit (which can be either the REFALS end-of-study visit or a separate baseline visit specifically for this study) are used as baseline values.

6.2.8 Multiple measurements

Here, a multiple measurement refers to a combination of analysis visit and timepoint where there are more than one value recorded for a given parameter.

If there are multiple measurements for a given parameter-visit-timepoint combination, values from the measurement that was performed last will be used.

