5.2.2 Dose adjustment

The levosimendan dose will be adjusted according to tolerability, including pulse/heart rate. It is recommended to reduce the daily dose of the study treatment (or discontinue the treatment if no further dose reduction is possible) if resting pulse/heart rate is repeatedly > 30 bpm more than the pre-treatment value or the subject has marked symptoms related to tachycardia (see section

6.4.4). It is further advised not to increase the dose at week 2 visit or any later time point if the resting pulse/heart rate change is close to this recommended limit.

After the initial two weeks of treatment with levosimendan 1 mg/day, changes in dose can take place at any time but it should be remembered that the full effect of a dose change may take 2 weeks to develop, at which point the subject should be reassessed before making any further dosing decision.

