6.1.2 Procedures during the treatment period

Visits will be performed either by telephone or attendance at the study centre. For simplicity, all visits of the same type involve the same procedures.

Any planned follow-up may take place at the study centre and may occur at any time, but should not be less frequent than every 3 months. The only fixed follow-up points are dose assessment at 2 weeks and telephone contact 6 weeks after start of the study treatment.

Any visit may be performed by telephone provided:

- A reliable measure of resting pulse/heart rate can be obtained and documented.
- The minimum 3-monthly study centre visit schedule is maintained.

In case a subject is no longer able to travel to the study centre, but levosimendan is considered to still be of clinical value, wholly remote monitoring by telephone contacts may be acceptable. This must be agreed in advance by the sponsor and the medical monitor, and an acceptable method of dispensing study treatment must be established.

Procedures during visits are presented in [Table 2](#). The morning dose of study treatment will be administered at the study centre during the study centre visit days. In addition, additional visits or contacts approximately 2 weeks after dose change can occur at any time (see section [6.1.3](#)).

Table 2. Procedures during the treatment period

Time	Study centre visit ¹	Telephone contact
Weight	x	
Pulse/heart rate and BP	x	Pulse/heart rate only
12-lead ECG	x	
Pregnancy test for females of childbearing potential	x	
SVC supine and sitting	x ²	
Study treatment	x	
ALSFRS-R	x	x
Borg CR10 scale	x	
Use of health care and home care resources use and non-medical assistive devices	x	x
Assessment of suicidality	x	x
Status for NIV support, invasive mechanical ventilation by intubation or tracheostomy and survival	x	x
AEs and SAEs	x	x
Medical history and current medical conditions	x	x
Concomitant treatments	x	x

¹ All procedures will be performed pre-dose

² MasterScope used up to 3 months

During the telephone contact a caregiver can take the telephone contact on behalf of the subject in case the subject is unable to communicate verbally due to disease progression.

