6.1.3 Additional visits

Additional centre visits or telephone contacts will be performed after changing the dose of the study treatment (see section [5.2.2](#)), approximately 2 weeks after the dose change. Procedures at these visits/contacts will be the same as described in [Table 2](#).

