6.2.9 Multiple timepoints

Visits following the Week 2 (and possible Week 4) site visit(s) and the Week 6 TC will be binned based on time elapsed since the baseline visit; visits falling into the same interval of time will be given the same label for reporting. The binning will be done on a monthly level, with visit days rounded to the nearest full month, using a conversion factor of 1 month = 30.4375 days.

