7.9.3 Laboratory values

Laboratory variables are not collected as part of the regular study visits. However, baseline values from the REFALS end-of-study visit will be summarised with descriptive statistics. See [REFALS SAP](#) for further definitions.

7.9.4 12-lead ECG

Descriptive statistics of standard 12-lead ECG variables and abnormal ECG findings will be tabulated by treatment group for each study visit.

Disjoint comparisons of heart rate changes from baseline to the thresholds of > 20 bpm and > 30 bpm will be summarised by treatment group at each study visit.

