7.9.5 Vitals signs

Descriptive statistics of subject weight, BMI, vital signs (i.e. pulse rate and both systolic and diastolic blood pressure in supine position) will be tabulated by treatment group for each study visit.

Descriptive statistics will also be reported for the following categorised measurements:

- systolic blood pressure:
 - < 90 mmHg and a decrease of ≥ 20 mmHg
 - > 140–160 mmHg and an increase of ≥ 20 mmHg
 - > 160 mmHg and an increase of ≥ 20 mmHg
- diastolic blood pressure:
 - < 60 mmHg and a decrease of ≥ 20 mmHg
 - > 90–100 mmHg and an increase of ≥ 20 mmHg
 - > 100 mmHg and an increase of ≥ 20 mmHg
- pulse rate:
 - < 60 bpm and a decrease of ≥ 15 bpm
 - > 100 bpm and an increase of ≥ 15 bpm
- change from baseline body weight:
 - a decrease of:
 - > 7–10%
 - > 10–20%
 - > 20%
 - an increase of:
 - > 7–10%
 - > 10–20%
 - > 20%

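### After Week 6, monthly binning with a keep-the-last rule can drop the high heart-rate reading that prompted a dose reduction, and no on-treatment maximum row is stated to recover it (minor)

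*SAP*

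**What the plan says.** **Labels and duplicates.** Under SAP 6.2.9 the Week 2 visit, a possible Week 4 visit and the Week 6 telephone contact stand apart. Later visits are rounded to the nearest month, and "visits falling into the same interval of time will be given the same label for reporting". SAP 6.2.8 defines duplicates by parameter, analysis visit and timepoint, and settles them as follows: "If there are multiple measurements for a given parameter-visit-timepoint combination, values from the measurement that was performed last will be used".

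**Heart-rate tables.** For the ECG, SAP 7.9.4 states: "Disjoint comparisons of heart rate changes from baseline to the thresholds of > 20 bpm and > 30 bpm will be summarised". That table is split by arm and is explicitly per visit. For vital signs, SAP 7.9.5 gives by-visit descriptive statistics and then adds: "Descriptive statistics will also be reported for the following categorised measurements". The only upper pulse category is "> 100 bpm and an increase of ≥ 15 bpm"; the lower one is < 60 bpm with a fall of at least 15 bpm. The SAP does not say whether these categories are per visit or at any time. Neither section mentions a maximum or an ever-exceeded row.

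**Clinical context.** Protocol 5.2.2 recommends reducing the dose if the "resting pulse/heart rate is repeatedly > 30 bpm more than the pre-treatment value", among other grounds. Protocol 6.1.3 places the follow-up visit or contact "approximately 2 weeks after the dose change". It may be by telephone, and for telephone contacts Protocol Table 2 lists "Pulse/heart rate only", with no ECG.

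**The concern.** A reading high enough to prompt a dose reduction is the one a heart-rate safety table most needs to show. The reassessment that follows is taken on the reduced dose and is timed so that it often falls in the same month. The keep-last rule then reports the second reading and omits the first.

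Long-term safety is the primary objective (Protocol 2.1), and Protocol 1.3.2 names increased heart rate as a potential risk. What is at stake is the measured counterpart to investigator-reported events: how many subjects ever crossed a heart-rate threshold while on treatment.

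A related gap lies in the pulse categories. The change component of 15 bpm counts only jointly with a level above 100 or below 60 bpm. No pulse category therefore rests on change alone at the protocol's own > 30 bpm figure.

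**Working it through.** **Inputs.** Month length 30.4375 days (SAP 6.2.9); this equals 365.25/12 exactly. Reassessment about 14 days after a dose change (Protocol 6.1.3). Visits from Day 43 on are binned, because Weeks 2, 4 and 6 keep their own labels. I take the analysis visit of 6.2.8 to be the label of 6.2.9, which is the natural reading but is not spelled out.

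**Label.** Month = floor(day/30.4375 + 0.5). Month 3, for example, runs from (3 − 0.5) × 30.4375 = 76.1 to (3 + 0.5) × 30.4375 = 106.5 days.

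**Same-label share.** For a gap of g days between the high reading and the reassessment, random timing gives 1 − g/30.4375. I also counted every start day from 43 to 365 (323 days).

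| Gap g (days) | Random timing | Counted |
|---|---|---|
| 12 | 0.606 | 200/323 = 62% |
| 14 | 0.540 | 180/323 = 56% |
| 16 | 0.474 | 159/323 = 49% |
| 21 | 0.310 | 104/323 = 32% |

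The 12 and 16 day rows are an assumed range around two weeks. The 21 day row assumes that the reduction comes a week after the high reading, with no other high reading nearer the change.

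**Visits at exact 13-week steps (assumption).** Days 91 and 105 are both Month 3, Days 182 and 196 both Month 6, Days 273 and 287 both Month 9, and Days 364 and 378 both Month 12. At these visits a 14-day reassessment always shares the label.

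**Illustration (assumed values).** Baseline 70 bpm; Day 91, 105 bpm (+35); dose reduced; Day 105, 80 bpm (+10). Month 3 reports +10. Both the > 30 bpm change and the > 100 bpm category disappear from that label.

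**Which tables are affected.** The rule works per parameter. A telephone reassessment without an ECG replaces the pulse value but not the ECG heart rate, so the ECG table is affected only when the reassessment includes an ECG. The pulse categories are affected if they are read by visit.

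**Pulse-change gap.** From baseline b, a rise above 30 bpm that ends at or below 100 bpm runs from 31 to 100 − b. This range is non-empty only for b ≤ 69. At b = 60 it is 31 to 40 bpm; at b = 65 it is 31 to 35 bpm.

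**End-of-study visit.** It falls 14 to 25 days after the last dose. Let L be the days from the last on-drug visit to the last dose. The chance that the end-of-study value shares that visit's label is the mean over g = 14 to 25 of max(0, 1 − (L + g)/30.4375). This is 0.359 at L = 0 and 0.135 at L = 7. Averaged over L = 0 to 91 it is 2.5%, and over L = 0 to 28 it is 8% (both spreads are assumptions).

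**The case against.** The strongest reply is that the signal is carried elsewhere. Adverse events are reported in full, and an event leading to dose reduction counts as an other significant adverse event (Protocol 6.4.1.1). Increased heart rate and palpitations are events of special interest with dosage changes tabulated (SAP 7.9.2), and dose-change groups are reported (SAP 7.4). None of this passes through the month bins, and all of it stands. A reader might infer that tachycardia vanishes from the report; the documents do not support that.

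Other points also stand, in whole or in part:

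- **Direction.** One might infer that the tables are biased towards safety. But after a late dose increase the same rule keeps the reading on the higher dose, so no net direction is shown.
- **Pulse categories.** It would be wrong to say that no category contains a pulse change, since SAP 7.9.5 has two that require 15 bpm. It would also be wrong to say that the pulse categories cannot give an ever-exceeded count, because their basis is not stated. That limit holds for the ECG table, which is explicitly by visit.
- **Partial cover.** Protocol 8.4.5.2 plans changes from baseline in pulse, and SAP 6.2.15 includes the maximum. Together these would show a large rise under its label. They give no count of subjects, though, and do not restore a value already replaced. At centre visits, and at COVID-19 replacement telephone visits with an ECG, the ECG table can also capture the rise. The pulse gap therefore matters mainly at ordinary telephone contacts.
- **Timing.** The trigger is a repeated rise, and Protocol 6.4.4 asks for re-checks where possible before a dose decision. The gap may thus exceed two weeks, which is why the 21 day figure is shown.
- **End-of-study visit.** Read literally, SAP 6.2.9 gives it a month label. But SAP section 2 names it separately, so a separate label is the likelier intent. A reader might infer that off-drug values routinely replace on-drug ones; on the assumptions above that is uncommon.

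By-visit tables are a legitimate descriptive choice in an uncontrolled study whose reporting was deliberately narrowed (SAP 7.11). That argues for keeping them. It does not supply the missing count.

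**Conclusion.** The point holds as a minor weakness. For readings after Week 6, SAP 6.2.8 and 6.2.9 together remove a high value from the by-visit tables when the reassessment shares its month. Given a late reduction, that is about half the time (49% to 62%) for gaps of 12 to 16 days and about a third (32%) for 21 days. These shares rest on the assumed gaps, on start days spread evenly over Days 43 to 365, and on the analysis visit being the month label. The documents give no rate of late dose reductions, so the number of subjects affected is unknown.

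The effect is established for the ECG > 20 / > 30 bpm table when the reassessment includes an ECG. It is conditional for the pulse categories. The lack of a pulse category based on change alone is a narrow gap, limited to baselines of 69 bpm or less. The end-of-study label needs clarifying and is not shown to be an error.

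**What to change.** Keep the by-visit tables and make two additions to the SAP:

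1. A per-subject on-treatment maximum (ever exceeded) row for the ECG heart-rate and pulse thresholds, drawn from all scheduled, unscheduled and telephone on-treatment records before the keep-last rule is applied.
2. The > 20 and > 30 bpm change categories applied to pulse rate in that row, alongside the existing pulse categories.

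As a clarification only, state that the off-drug end-of-study visit keeps its own post-treatment label outside the month bins.

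The cost is a few sentences and a few table rows from data already collected. The downside is that a maximum includes some transient readings and will look less favourable than the by-visit figures; a footnote can say so. No clinical rule changes.
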